Rationale: Evidence-based treatments for posttraumatic stress disorder (PTSD), such as Eye Movement Desensitization and Reprocessing (EMDR) and Imagination and Rescripting Therapy (ImRs), are highly effective treatments in the majority of the PTSD patients. PTSD is highly comorbid with personality disorders (PD), especially borderline personality disorder (BPD), and cluster C - avoidant, dependent, or obsessive-compulsive - personality disorders (CPD). It is not clear yet what treatment is most effective for those who suffer from both PTSD and PD. There is growing motivation in clinicians to offer PTSD treatments to PTSD with comorbid PD, because these treatments are highly effective, relatively short (weekly sessions, 3-6 months) and there is some evidence that with PTSD treatment, comorbid PD symptoms might resolve as well. PTSD treatments are less time-consuming than PD treatments and - at least in the short term - financially attractive. However, at least 30-44% PTSD patients do not sufficiently respond to these treatments. Moreover, a high number of PTSD patients are excluded from these therapies because of suicidality, self-destructive behaviour or other personality problems. Therefore, it might be more efficient to add a PD treatment at the same time. Evidence-based treatments for personality disorders (PD), such as dialectical behaviour treatment (DBT) for BPD, and schema-focused treatment (SFT) for CPD are well established. These treatments are more intensive (twice a week for at least one year) than PTSD treatments. There is some evidence that integrated PTSDPD treatment is twice as effective on reducing PTSD symptoms than PD treatment alone, but integrated PTSD-PD treatment is not yet directly compared to PTSD treatment alone. This study will address this knowledge gap, including secondary outcome measures on functioning, quality of life and cost-effectiveness.

The result of this study might be that one or the other treatment works better, depending on the personal profile of the patient. So far, some psychological factors have been found

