3. STUDY DESIGN

The design of this study consists of two – connected - RCTs comparing PTSD-treatment to integrated PTSD-PD treatment in patients with PTSD and comorbid PD in a specialized treatment setting (figure 2):

A1. EMDR versus integrated DBT-EMDR, and

A2. ImRs versus integrated SFT- ImRs.

Assessment points are: baseline (T₀), after 3 months (T₁), after trauma treatment has finished, around 6 months (T₂), 3 months after T₂ (T₃), after 12 months (T₄) and at 18 months (follow-up, FU).

PTSD treatments specifically address the troubling memories of the traumatic event and the personal meaning of the event and consist of 12 to 18 sessions in maximum 6 months, and are:

- EMDR (Eye Movement Desensitization and Reprocessing)

EMDR was developed in 1987 by Shapiro (De Jongh & Ten Broeke, 1998). In EMDR the therapist induces a bilateral stimulation once the client has focused the attention on a disturbing image or memory related to the traumatic experience. The bilateral stimulation is induced by the movement of the therapist's fingers in front of the patients face from

the left to the right with the instruction for the client to follow this movement of the hand with the eyes. Attention is drawn to what traumatic memory and the dysfunctional thoughts about it are currently doing with the patient and not to what the patient was thinking during the traumatic experience.

- ImRs (Imagination and Rescripting Therapy) (Arntz et al., 2007, Raabe et al., 2015).

In ImRs, the patient imagines the (onset of a) traumatic experience and subsequently changes the original course of events by imagining different interventions and outcomes, thereby allowing for the change of original schematic representations and cognitions (Hackmann et al., 2011). ImRs implies changing the traumatic imagery in fantasy, to produce a more favourable outcome (without denying the trauma), imagining having control over the situation and being able to act according to one's needs, to express one's feelings and action tendencies. ImRs was hypothesized to alleviate PTSD symptoms as well as change trauma-related beliefs and schemas (e.g. powerlessness, victimization, and inherent badness). It is suggested that ImRs might be more effective in patients with emotions and cognitions like anger, irrational guilt, shame disgust and/or self-contempt (Arntz et al., 2007).

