Integrated PTSD-PD treatment consist of a PTSD treatment interwoven in a PD treatment that takes at least twice sessions per week, for the duration of one year:

- DBT (Dialectical Behavior Treatment), a manualized outpatient cognitive-behavioral treatment with two components: (a) weekly individual therapy and (b) weekly group skills training. Individual sessions focus on a hierarchy of target behaviors, which the patient tracks on a daily basis with diary cards. Behavioral analyses of the pattern and chain of thoughts, emotions, and events take place routinely to help the patient identify triggers and alternative strategies for coping. Change strategies such as problem solving and reinforcement techniques are used in combination with acceptance and validation of the patient's experience. Group skills' training is used to help patients develop less self-destructive and more adaptive means of coping with intolerable affects. These skills include awareness of emotions and reactions, interpersonal effectiveness, emotion regulation, and distress tolerance. Skills are then integrated into the individual treatment in problem situations, e.g. suicidal urges (Linehan, 1993).

- SFT (schema focused treatment) is a form of psychotherapy integrating cognitive therapy, behavior therapy, object relations, and gestalt therapy into one unified,

systematic approach to treatment. The focus in SFT is on changing maladaptive schemes that patients develop early in life and thereby improve emotion regulation skills. Change is achieved through a range of behavioral, cognitive, and experiential techniques that focus on (1) the therapeutic relationship, (2) daily life outside therapy (also through homework assignments), and (3) past (traumatic) experiences (Young et al., 2003). Psychomotor therapy (PMT) is part of the SFT treatment protocol.

[figure not shown]
In the Sinai Centrum, 2 “Zorgpaden” will be implemented in Fall2017:

“Zorgpad 1” with EMDR or ImRs (3-6 months) and Zorgpad 2” with EMDR-DBT or ImRs - SFT (9-12 months). Therapists need to be “adherent-to-the model”, which will be ascertained by regular supervision with audiovisual recordings based on the different theoretical psychotherapeutic principles and therapies are delivered by protocol. At this moment, there is no clear scientific evidence and criteria are not explicitly defined for the one or the other treatment, except that patients with PTSD without comorbid PD have to be indicated for “Zorgpad” 1.

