Use of co-intervention: Patients may continue taking medication for PTSD throughout the study. Patients who started with new medication for PTSD within 1 month prior to the initial screening will be excluded from participation. No other psychological or new pharmacological therapy is allowed during treatment. Medication use is monitored during the study.

Escape medication/treatment: Participants might start taking medication or another form of treatment/therapy in case of acute crisis during the study. The use of these medications or crisis intervention during the study as co-intervention will not lead to exclusion from the study, but will be monitored, documented, and reported.

Further treatment: After completion of the EMDR or ImRs a first follow-up assessment will be completed and the therapist will see the patient for an evaluation. If more treatment is acutely needed, a clinical evaluation is done and the indication staff will decide what treatment to offer to the patient. The kind, intensity and frequency of this further treatment will be monitored, documented and reported. All patients in Zorgpad 1 are allowed to start SFT or DBT after T4 (i.e. 6 months after completing Zorgpad 1).

18

Figure 2. Flow chart for two connected randomized controlled trials (RCTs) for patients with PTSD and borderline personality disorders (BPD) resp. with PTSD and cluster C personality disorders (CPD)

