6.2.2. Serious adverse events (SAEs)

We do not expect any serious adverse event (i.e. any untoward medical occurrence or effect that results in death; is life threatening (at the time of the event); requires hospitalisation or prolongation of existing hospitalisation; results in persistent or significant disability or incapacity; is a congenital anomaly or birth defect; any other important medical event that may not result in death, be life threatening, or require hospitalization, may be considered a serious adverse experience when, based upon appropriate medical judgement, the event may jeopardize the subject or may require an intervention to prevent one of the outcomes listed above). The main reason for this is that all four treatments given in the RCTs are evidence-based for at least one of the disorders the patients suffer from (PTSD and PD) and patients who will be assigned to the PTSD-treatment only can given PD-treatment as well after T4 (after 6-12 months) within the research design.

Suicidality or self-injurious behaviour is very common in the study population included for this study. It is also known that starting a new treatment, such as EMDR or DBT could increase symptoms in the beginning, which can develop into suicidal behaviour. SAE's which will occur during the treatment and for which medical care is needed, will be reported to the accredited METC. To monitor the SAE's, patients will be asked to fill in a self-injury questionnaire (*Opzettelijk zelfverwondend gedrag, Baetens & Claes 2014 based on The Brief Non-Suicidal Self-Injury Assessment Tool (BNSSI-AT) van Janis Whitlock en Amanda Purington (2013)*) at the regular assessments. In case of SAE's for which medical care is needed, in between the assessments, therapists will report these incidents to the researchers at the weekly consultations, whom will report these to the accredited METC. The sponsor will report SAEs to the accredited METC that approved the protocol, within 7 days of first knowledge for SAEs that result in death or are life threatening followed by a period of maximum of 8 days to complete the initial preliminary report. All other SAEs will be reported within a period of maximum 15 days after the sponsor has first knowledge of the serious adverse events.

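### Section 3 equates T4 (month 12) with six months after completing Zorgpad 1; the two agree only for completion at month 6, so the parenthesis should be corrected

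*Combined protocol and SAP*

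**What the plan says.** The rule is in section 3, Further treatment: "All patients in Zorgpad 1 are allowed to start SFT or DBT after T4 (i.e. 6 months after completing Zorgpad 1".

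The surrounding text fixes the dates that this rule depends on:

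- Section 3 lists the last two assessments as "after 12 months (T₄) and at 18 months (follow-up, FU". T4 is thus counted from baseline and not from the end of trauma treatment.
- Section 3 describes Zorgpad 1 as a pathway "with EMDR or ImRs (3-6 months", and says that the PTSD treatments "consist of 12 to 18 sessions in maximum 6 months".
- The Summary (Intervention) gives both PTSD-only arms 3 to 6 months of treatment followed by a pause of 6 to 9 months, against 12 months of integrated treatment.
- Section 6.2.2 states the same permission again: PTSD-only patients "can given PD-treatment as well after T4 (after 6-12 months) within the research design".
- On other therapy, section 3 says: "No other psychological or new pharmacological therapy is allowed during treatment". It also keeps a clinical exception: "If more treatment is acutely needed, a clinical evaluation is done and the indication staff will decide what treatment to offer".

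The Summary sets the primary outcome as PTSD severity at 12 months. Section 7.1 analyses the CAPS-5 at T0, T2 and T4.

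**The concern.** The sentence presents two dates as the same date. One is an assessment fixed to the calendar. The other moves with the patient's own completion date. A patient who finishes trauma treatment before month 6 reaches the second date before the first.

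The rule says when the PTSD-only arm may receive DBT or SFT, and that component is what separates the arms. If staff worked from the parenthesis, a faster completer could start it before the month-12 CAPS-5. If integrated treatment works as the protocol hypothesises, that would narrow the primary contrast. The co-intervention ban does not clearly close the gap, because it is worded for the period of treatment and the interval at issue is the pause after it.

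**Working it through.** **Inputs.** T4 = month 12 (section 3). Zorgpad 1 duration d = 3 to 6 months (section 3). Pause of 6 to 9 months (Summary). The lag L from T0 to the first session is not given. Section 5.3 places the baseline MRI visit within two weeks of T0 and before treatment starts, so L need not be zero. I take 0, 0.5 and 1 month as assumed values.

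**Step 1: reproduce the plan's own figure.** With L = 0, the wait from completion to month 12 is 12 − d:

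- d = 3, 4, 5, 6 gives 9, 8, 7, 6 months.

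This is exactly the Summary's range of 6 to 9 months, so the Summary and the words after T4 describe the same date. The parenthesis keeps only the lower end of that range.

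**Step 2: date the parenthesis.** Its date is L + d + 6. The gap before T4 is max(0, 12 − (L + d + 6)) = max(0, 6 − d − L).

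| Lag L (assumed) | d = 3 | d = 4 | d = 5 | d = 6 |
|---|---|---|---|---|
| 0: date (gap) | 9 (3) | 10 (2) | 11 (1) | 12 (0) |
| 0.5: date (gap) | 9.5 (2.5) | 10.5 (1.5) | 11.5 (0.5) | 12.5 (0) |
| 1: date (gap) | 10 (2) | 11 (1) | 12 (0) | 13 (0) |

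The two dates agree only when completion, d + L, falls at month 6 from baseline. Within the stated 3 to 6 months, the largest gap is 3 months.

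**Step 3: is completion before month 6 foreseen?** The stated range of 3 to 6 months already says so. The Summary also calls PTSD treatments in general "relatively short (weekly sessions, 3-6 months". Section 3 gives no session frequency, so a weekly pace in this trial is an assumption. Under it, 18 sessions take 18 / 4.348 = 4.1 months. The parenthesis then falls at month 10.1 + L, a gap of 1.9 − L: 1.9, 1.4 or 0.9 months for the three lags. Twelve weekly sessions would take 12 / 4.348 = 2.8 months, which is below the protocol's own 3-month minimum, so I do not extend the range to it.

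**Step 4: check the section 6.2.2 parenthesis.** Its 6 to 12 months has no stated starting point. Counted from baseline it spans months 6 to 12. Counted from completion it spans 3 + 6 = 9 to 6 + 12 = 18. Both ranges contain month 12, so this wording is loose but does not contradict T4.

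**Step 5: check against the extra contact.** Section 5.3 gives PTSD-only patients a contact 3 months after T3. T3 is 3 months after T2, and T2 follows directly on trauma treatment. The contact therefore falls about 6 months after completion, which is the date in the parenthesis. Its purpose includes a reminder of measurements still to come. For an early completer, then, the plan itself places T4 later than 6 months after completion.

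**The case against.** The strongest reply is that the operative words are already right. The sentence says after T4, T4 is defined as month 12, and section 6.2.2 repeats after T4. The Summary makes the pause to month 12 part of the intervention. The parenthesis also fits the nominal timetable, in which trauma treatment ends near month 6 and 6 + 6 = 12. Figure 2 is not shown in the text available and may state the timing. Harm needs staff to follow the parenthesis over the named assessment. Further treatment given for acute need is documented, and the Tic-P records health care use at T4, so an early start would not necessarily go unseen.

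Most of this stands. It settles the intent and limits the point to wording. It does not make the equivalence true: the sentence tells staff that the two dates are one, and for a completer before month 6 they are not.

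A reader might infer two stronger points, and the documents support neither. The first is that the plan schedules an early crossover. After T4, read alone, forbids an earlier start, and the pause in the Summary agrees with it. The second is that this sentence is the only text dating routine DBT or SFT in the PTSD-only arm. Section 6.2.2 and the Summary date it too.

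**Conclusion.** The point holds as a minor error: a wrong equivalence inside an operative rule, where the rest of the protocol shows that month 12 is meant. Its size is a matter of dates only, at most 3, 2, 1 or 0 months before the primary CAPS-5 for courses of 3, 4, 5 or 6 months. These are upper bounds, because any lag before the first session shortens them.

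A reader might go on to infer that the primary contrast is biased. The documents give neither a distribution of completion times nor a rate of early starts, so no effect on the CAPS-5 difference can be estimated and none is claimed. Any consequence depends on staff acting on the parenthesis in place of the words before it.

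**What to change.** In section 3, keep the words after T4 and replace the parenthesis so that the rule reads in substance: *at month 12 after baseline (about 6-9 months after completing Zorgpad 1), after the T4 assessment or, if T4 is missed, once its due date has passed.* Two details matter:

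- Month 12 should govern and the interval should be marked as approximate. With a 1-month lag, the wait from completion to month 12 is 12 − 6 − 1 = 5 to 12 − 3 − 1 = 8 months.
- The clause on a missed T4 is needed so that a patient who skips the assessment is not barred from treatment.

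Keep the acute-need and crisis exceptions as they are.

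Two optional additions: align the loose interval in section 6.2.2 with the same wording, and record the start date of any further treatment beside the type, intensity and frequency that section 3 already documents.

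The cost is one sentence, or two with section 6.2.2, and at most one date field. No visit, measurement or analysis is added.

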4. STUDY POPULATION

4.1 Population

The study population consists of all patients between 18-65 years old, referred to the SC with comorbid PTSD and PD, who are willing to participate in the study (informed consent); N = 252 patients (see 4.4), of which sub-group of 80 patients (N = 40 Condition 1 + 40 Condition 2) will participate in the MRI study (before and after treatment). For baseline MRI comparison, extra 40 healthy controls, matched on age, gender and educational level, will be recruited also for the MRI study via advertisements in local newspapers and through hersenonderzoek.nl. In total, 292 persons will be included in this study.

A pilot episode will be introduced (September – December 2017) to test the feasibility of the study and inclusion rate. Feasibility is enhanced by the opportunity to build on the established expertise of the academic research group in Arkin – Research and VUmc in conducting effect studies, longitudinal and neurobiological studies.

4.2 Inclusion criteria

In order to be eligible for study participation as a patient, he/she has to be at To:

- Diagnosed with PTSD (309.81), and
- Diagnosed with a personality disorder (301.81 borderline, 301.4 obsessive-compulsive, 301.6 dependent, 301.82 avoidant), or at least the number of required symptoms minus 1 for at least one of those PDs (i.e. four symptoms for borderline, three symptoms for obsessive-compulsive, four symptoms for dependent, three symptoms for avoidant).

To be eligible for the study, both patients and healthy controls have to:

- Be aged between 18 and 65 years
- Give written informed consent
- Speak / understand Dutch sufficiently

4.3 Exclusion criteria

A patient who meets any of following criteria will be excluded from participation in this study:

- Current psychosis
- Comorbidity interfering with treatment or randomisation (severe outward aggression, antisocial PD, treatment interfering addiction or eating disorders, somatic problems)
- Primary diagnosis of paranoid, schizoid, schizotypal, narcissistic, histrionic or antisocial PD
- Mental retardation

For the healthy controls, current psychiatric diagnosis is an exclusion criterion.

For the subgroup of patients and controls that also undergo MRI examination more exclusion criteria are: Pregnancy; Metal implants (such as pacemakers, etc.); Somatic disorders interfering with brain functioning; Claustrophobia; Other psychopharmaca than at-least-3months stabile dose SSRI or low-dose benzodiazepines

4.4 Sample size calculation

A power calculation was made based on Twisk (2007). We assume that PTSD treatment (EMDR or ImRs) have a small effect size (< 0.5) in the complex patient group with PTSD and comorbid

CPD/BPD, while the integrated treatment will show double effect sizes (1.0) (Harned et al., 2014). With a minimal clinical relevant difference of a 0.5SD on the CAPS-5, and the assumptions of a SD of 20.0, an intra-person correlation coefficient of 0.7, 5 follow-up measurements, the needed number to include is 50 persons per condition to reach for 80% power. Expecting a drop-out rate of 25%, we will include 63 persons per arm, or for 4 arms in total 252 persons.

In 2016, approximately 950 new patients were referred to the SC (Amstelveen). From these patients, ca. 450 had PTSD. From these PTSD patients, 168 had a comorbid PD and 188 more were not assessed for personality traits (“Uitgestelde diagnose”). We expect that introducing the assessment of axis II assessments with this study will result in an estimated 300 patients with PTSD and PD per year, and after 33% refusals or exclusions, in an estimated 200 patients possible to include per year. To be sure to include enough patients, we will need to include more patients from another site of the

Sinai Center, i.e. Amersfoort (400 patients, from which 216 PTSD patients, from which an estimated 100 PTSD + PD patients), and extend the inclusion period.

From these 252 patients, 80 will be asked for additional MRI, next to 40 healthy controls (Total sample size = 292). An estimated 40 patients will be available for a second MRI after 6 months (total of 160 scan sessions).

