treatment (1.0), the number of persons needed to include is 50 persons per condition to reach for 80% power. Expecting a dropout rate of 25%, we will include 63 persons per arm, for 4 arms a total of 252 adult patients with PTSD and - at least 4 - PD symptoms. Of these patients, 80 next to 40 healthy matched controls will be asked for additional MRI research before and after treatment. In total, 292 persons will be included in this study.

Intervention: In patients with PTSD and BPD: EMDR (3-6 months plus 6-9 months treatment pause) compared to integrated DBT-EMDR (12 months); in patients with PTSD and CPD: ImRs (3-6 months plus 6-9 months treatment pause) compared to integrated ImRs-SFT (12 months).

Main study parameters/endpoints: Primary outcome measure is PTSD symptom severity after 12 months. Secondary outcome measures are PD symptoms (SCID-5-PD), disability (WHODAS), quality of life (EQ-5D-5L) and health costs (Tic-P). At baseline (T₀) and after 12 months (T₄) clinical interviews (CAPS-5, SCID-5-PD dimensional score) and self-rating scales (PCL-5) will be used. After 3 (T₁), 6 (T₂), 9 (T₃), and 18 months (follow-up), questionnaires only will be used. At baseline, candidate predictors will be measured including above mentioned cognitive, affective, relational factors, and hormonal and epigenetic factors. In a subgroup, structural and functional MRI, with resting-state and an emotion processing (face recognition) will be performed.

Nature and extent of the burden and risks associated with participation and benefits:

The burden and risks associated with participation in this study is reasonable. All patients will receive psychotherapy, which is considered to be the most effective treatment for PTSD and PD. There is evidence that all four conditions are therapeutic in patients with PTSD and PD and no evidence yet what condition is more effective. Total time of the six measurements is approximately 5 hours per patient for interviews and 5 hours for questionnaires (see table 3), which are partly part of the routine outcome measurements (ROM). Questionnaires can be filled in at home. On the one hand, extensive clinical interviews and self-rating scales can be felt as disturbing because of fatigue, taken time and emotional burden. On the other hand, patients may feel well recognized by the time taken by specialized clinicians for them. Assessors will be well-trained and work in close

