Blood samples will be collected in 3 x 6ml tubes and the frozen samples will be stored at -80°C for intended future assaying of inflammatory markers (see Coelho et al., 2014), neuropeptides (such as oxytocin, 5HT), and epigenetics (such as FKBP5-methylation, OXTR- & 5HTTLPRgenes). The tubes will be stored without personal data linked to it, and they will only be marked with a subject number as described in section 9.1. below. Cortisol level (HPA-indicator) will be assessed in hair. This sample can be collected non-invasively by cutting a 1-cm distal to the scalp (1 month's exposure) sample of hair (Russell et al., 2012). All samples will be stored for 15 years (according to Archiefwet 1995).

In a subgroup: MRI session

Exclusion criteria for MRI research will be checked (metal implants, pregnancy, somatic disorders interfering with brain functioning, other (psycho-)pharmaca than at-least-3-months stabile dose SSRI or low-dose benzodiazepines, claustrophobia). A separate visit for MR scanning will be planned within 2 weeks of To, before the start of treatment, without causing a delay in treatment start. MRI sessions take at maximum 60 minutes (30-min functional MRI with a face recognition, and a suppression vs. reappraisal task, 5-min structural MRI, 8-min resting state MRI; and 8-min DTI) plus 30 min preparation. Next to patients, 40 healthy control persons, matched for age, gender, and education, will be asked to participate in one MRI session (no repeat MRI). These healthy control persons will be recruited via advertisements in local papers.

T1, T3 and FU

Patients do not have to come to the study center for T1, T3 and FU and can fill in the questionnaires via a login code at home if they have access to the internet (see Table 1.). Child trauma and life events questionnaires are only done at baseline (CTQ, LEC-5). Total duration of these measurements (T1, T3 and FU) will be between 15 and 30 minutes (see Table 3).

T2 visit

From all participants whose blood and hair was collected at baseline, blood and hair will be collected at T2 as well (duration 30 minutes). All participants who participated in the fMRI study at baseline will have their second MRI at T2. (duration 90 minutes). At T2, the CAPS-5 will also be conducted and participants will fill out the same questionnaires as at T0, except for the CTQ and LEC-5. Total duration of these measurements of will be ca. 2 hours (see Table 3).

Extra contact moment

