5.6 Follow-up of subjects withdrawn from treatment

Patients who drop-out out of (part of) the treatment remain in the study and will still be asked to complete the follow-up measures. Priority will be given to the online assessment with the PCL-5 and OQ-45.

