7.1 Primary study parameters

For population description, the CAPS-5, M.I.N.I.-plus, SCID-5-PD, will be used in addition to the CTQ, LEC-5, DERS, ITQ, PAI-BOR, STAS, PSQI, DES-II, WAV, RSQ, CPI, BDI, AUDIT, WHODAS, EQ5D-5L, and Tic-P will be used (see Table 1). The subgroup of patients that underwent MRI will be compared to the rest of the group to test for pretreatment differences in PTSD severity and type/severity of PD.

The primary analysis in the RCTs will be improvement of PTSD symptoms at 3 time points. This primary analysis will include trauma symptom scores at T₀, T₂ and T₄ (CAPS-5, severity score) in a repeated measurements model, a linear mixed model for repeated measurements including at least time points, treatment group, the interaction between time point and treatment, sex, age and severity as fixed factors, baseline score as covariate and subject as random intercept factor. An cAR(1) structure will be used to model the residual covariance matrix. Responders will be defined as participants with a posttest score at least 1 SD below the pretest score (based on Jacobsen and Truax, 1991).

Secondary analyses will examine whether hormonal and epigenetic factors (5-HTTLPR, BDNF, cortisol/FKBP5-methylation, oxytocin/OXTR) mediate the treatment effects. Mediation analyses will include levels of the aforementioned variables on T₀ and T₂ to estimate the direct and indirect paths of casual treatment on the primary and secondary study parameters, through the proposed mediators.

For individual prediction analyses, machine learning techniques (in R: supervised and unsupervised techniques, e.g. the random forest model method) will be applied to separate treatment responders from non-responders based on clinical and neurobiological candidate predictors and in order to define the predictors

contributing most to classification accuracy, calculating sensitivity, specificity, and positive and negative likelihood ratios from the prediction model (Ball et al., 2014).

Candidate predictors that will be used are:

- Psychological factors: Cognitive factors (educational level/IQ, working memory, emotion regulation), Affective factors (hyperarousal: anger, sleep; hyperarousal: dissociation), and Relational factors (therapeutic alliance, attachment, social support);

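### Section 4.4 powers the CAPS-5 comparison on five follow-up measurements, but the CAPS-5 is repeated only at T2 and T4; 63 per arm also leaves 47, not 50, after 25% drop-out

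*Combined protocol and SAP*

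**What the plan says.** Section 4.4 sets the target difference at half a standard deviation on the CAPS-5, with an SD of 20.0 and a within-person correlation of 0.7. It then gives the remaining inputs and the result: "5 follow-up measurements, the needed number to include is 50 persons per condition to reach for 80% power". The allowance for loss follows: "Expecting a drop-out rate of 25%, we will include 63 persons per arm, or for 4 arms in total 252 persons". No alpha, sidedness or formula is printed; the section cites a textbook on longitudinal analysis.

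The CAPS-5 schedule appears in several places:

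- Section 7.1, primary analysis: "This primary analysis will include trauma symptom scores at T₀, T₂ and T₄ (CAPS-5, severity score".
- Section 5.3, T2 visit: "At T2, the CAPS-5 will also be conducted". For the other visits: "Patients do not have to come to the study center for T1, T3 and FU", since those questionnaires can be completed online at home.
- Table 1 marks the CAPS-5 three times in all. Table 3 gives interview minutes at T0, T2 and T4 and none at T1, T3 or FU.
- The Summary places the CAPS-5 interview at T0 and T4 and says of the other visits: "After 3 (T₁), 6 (T₂), 9 (T₃), and 18 months (follow-up), questionnaires only will be used". It also states: "Primary outcome measure is PTSD symptom severity after 12 months".

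**The concern.** Sections 5.3 and 7.1 and Tables 1 and 3 give two CAPS-5 scores after baseline, and the Summary gives one. Nothing in the plan gives five. Five post-baseline measurements is the schedule of the PCL-5, which section 5.1.2 lists as a secondary outcome. Counting baseline as one of the five does not help, because the CAPS-5 is taken only three times in total.

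The number of follow-ups feeds directly into the sample size: averaging more repeated scores reduces variance, so too high a count gives too small an N. The inflation for drop-out looks wrong in the same direction, because 50 appears to have been multiplied by 1.25 instead of divided by 0.75. What is at stake is whether the stated 80% power applies to the primary analysis described in 7.1.

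**Working it through.** **Inputs.** From section 4.4: SD 20, difference 10 (0.5 SD), within-person correlation ρ = 0.7, 80% power, 25% drop-out, 63 per arm. Assumed: two-sided 5%, which fits the stated result better than one-sided 5% (38 per arm with five follow-ups).

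**Formula.** Section 4.4 prints none, so this is a reconstruction. For a mean difference over T follow-ups, the variance factor is v = [1 + (T − 1)ρ]/T, and

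n per arm = 2 × (1.96 + 0.8416)² × v / 0.5² = 62.79 × v.

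Power = Φ(0.5/√(2v/n) − 1.96).

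| CAPS-5 follow-ups | v | n per arm for 80% | Power, n = 50 | Power, n = 47 |
|---|---|---|---|---|
| 5 (section 4.4) | 3.8/5 = 0.76 | 47.7 → 48 | 81.8% | 79.4% |
| 2 (T2 and T4) | 1.7/2 = 0.85 | 53.4 → 54 | 77.4% | 74.8% |
| 1 (T4 only) | 1.00 | 62.8 → 63 | 70.5% | 67.9% |

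The first row comes within two of the plan's 50 per condition, so the plan's figure is approximately reproduced with five follow-ups.

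**Drop-out.** 50 × 1.25 = 62.5, rounded up to 63. But 63 × 0.75 = 47.25, so about 47 remain. Keeping 50 requires 50/0.75 = 66.7, or 67 per arm. With five follow-ups, 47 per arm still gives 79.4%, so this slip alone costs about 0.6 points against the 80% target. Moving from five follow-ups to two at 50 per arm costs 81.8 − 77.4 = 4.4 points.

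**With the baseline covariate of 7.1.** Adjustment reduces the variance factor to v − r₀², where r₀ is the correlation between baseline and follow-up CAPS-5, taken as equal for T2 and T4. Section 4.4 does not state r₀, so a range is shown. Power with 47 per arm:

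| Assumed r₀ | Mean of T2 and T4 | T4 only |
|---|---|---|
| 0.3 | 79.4% | 71.9% |
| 0.5 | 87.9% | 79.9% |
| 0.7 | 98.1% | 92.4% |

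For 80% at n = 47 the variance factor must be at most 47/62.79 = 0.7485. This gives r₀ = √(0.85 − 0.7485) ≈ 0.32 for the mean of T2 and T4, and r₀ = √(1 − 0.7485) ≈ 0.50 for T4 only.

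**The case against.** The strongest reply is that the planned analysis may have ample power. Section 7.1 includes baseline score as a covariate, and if the stated 0.7 also held between baseline and follow-up, 47 per arm would give 92% to 98%. This stands as a reason not to call the trial underpowered. It does not repair section 4.4, which states neither that correlation nor any credit for adjustment. The correlation may also be lower over 6 to 12 months, given the autoregressive residual structure in 7.1.

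Second, it is not proven that five follow-ups produced the 50. The same formula gives 48.7 for four measurements and 50.2 for three, and three is the total number of CAPS-5 scores. The origin of the 50 is therefore uncertain. The printed input is not: it says five follow-ups, and baseline is not a follow-up.

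Third, 47 is a worst case. The mixed model uses partial data, section 5.6 keeps treatment drop-outs in the study, and 4.4 does not say whether its 25% means stopping treatment or losing outcome data. That is fair, but the relief is limited. For those patients section 5.6 says: "Priority will be given to the online assessment with the PCL-5 and OQ-45", and neither measure enters the primary model. Section 5.4 sets the same priority for early leavers who will not complete everything.

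Fourth, the figures for the mean of T2 and T4 assume the same 0.5 SD effect at both visits, although the integrated treatment is still under way at T2. Section 7.1 does not name an averaged contrast. This too is fair, and it is why the T4-only figures are needed as well.

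**Conclusion.** The point holds. An input printed in section 4.4 contradicts the CAPS-5 schedule in the rest of the plan, so the stated 80% does not describe the primary analysis in 7.1. Without baseline adjustment and with 47 per arm, power is about 75% for two follow-ups and 68% for T4 alone. Most of that shortfall comes from the follow-up count and little from the drop-out slip. With baseline adjustment, power may be well above 80% or somewhat below it, depending on a correlation the plan does not give.

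These figures rest on the reconstructed formula, a two-sided 5% level, complete loss of 25%, and an equal effect at T2 and T4 where the two are averaged. The error should be corrected, but it does not show that 252 patients are too few.

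**What to change.** Keep 63 per arm and 252 in total. In section 4.4, and in the Summary where it repeats the result:

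- Replace the five follow-up measurements with the two CAPS-5 follow-ups (T2 and T4) used in 7.1.
- State alpha and sidedness.
- State that 25% complete loss leaves about 47 evaluable per arm.
- Restate power for the baseline-adjusted model over a small range of baseline correlations, for example 0.3, 0.5 and 0.7. Give the T4-only figures beside those for T2 and T4, because the Summary names 12 months as the primary outcome.

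Reconcile the Summary's questionnaire-only description of T2 with Table 1 and sections 5.3 and 7.1.

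The cost is wording and one recalculation, with no extra patients, visits or analyses. The sponsor should expect the restated power for a T4-only contrast to fall below 80% if the assumed baseline correlation is under about 0.50.
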